 Quality (Clinical, Educational, etc)												
3.1.05	Does the proposal require the use of information which can identify or potentially identify individuals?	No										
3.1.06	Access is being requested to data from which sources? (tick as many as are relevant)											

- A single NHS Scotland Board (excluding NSS)
- NHS National Services Scotland
- More than one NHS Scotland Board
- A national NHS Scotland system/database
- More than one NHS Scotland system/database
- Community Health Index (CHI) database
- NHS Central Registry

If other, please give details:

**3.1.07** *Provide a full, clear concise outline of the proposal background – describe why it is needed, aims and objectives and envisaged benefits to the public and/or patients:*

Adhesion formation is the most common cause for long – term complications in abdominal surgery. Abdominal surgery is performed by a multitude of specialists, including general surgeons, gynaecologists, vascular surgeons and urologists. In Scotland, like many other developed countries, adhesion- related complications cause a huge burden of morbidity. Adhesion-related complications comprise various clinical entities such as small bowel obstruction, chronic pain and female infertility.

In 1999 [name] demonstrated in the SCAR studies, using data from the Scottish National Health Service record linkage database, that as many as 34.6% of patients undergoing abdominal surgery are readmitted for complications directly or possibly related to adhesion formation in 10 years after surgery.

Since this landmark study a number of strategies were introduced to reduce adhesion formation. First are the so-called 'anti-adhesion' barriers. Almost simultaneously there has been the rise of minimal invasive surgery. Minimal invasive surgery is associated with less extensive peritoneal injury and adhesion formation.

While minimal invasive surgery became adopted quickly, the use of anti-adhesion barriers remains marginal. Many surgeons therefore feel that with laparoscopy further adhesion prevention is not necessary, despite some evidence that incidence of adhesion- related complications is still considerable.

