	
To evaluate the impact of laparoscopic surgery on adhesion- related formation, we are planning to perform an update of the SCAR studies to recent years in which a large number of laparoscopic surgeries have been performed. Comparison of readmissions for adhesion- related complications after open and laparoscopic surgery will be made. The study will provide an estimate of the current burden of adhesion-related morbidity in Scotland, which could also serve as a model for the current burden in other European countries. Further such estimate can be used to model the impact of further implementation of anti-adhesion barriers on adhesion-related morbidity and healthcare costs in both Scotland and abroad.

3.1.08	
Provide a full, clear and concise outline of the proposal design, listing: data sources; sample size ; inclusion/exclusion criteria (eg involvement in trial/survey; health event, etc); relevant date range; need for identifiable or potentially identifiable data; requirement for a matched control cohort etc.
 
We intend to use the Scottish National Health Service record linkage capabilities. Inclusion criteria are all patients undergoing initial abdominal or pelvic surgery between June 2009 and June 2011. Selection will be made by OPCS-4 codes related to the admission. A list of relevant codes can be found in the appendix. We choose for these years to allow inclusion of an incident population in a time that laparoscopic surgery had already been implemented and that allows for 4 to 5-years of follow-up.
 
We will exclude patient who had had abdominal or pelvic operation in the 5 years before 2009, as pre-existing adhesions from this prior surgery might influence results. There are no further exclusion criteria.
 
For analyses patients will be grossly divided in three groups of anatomical location of the surgery: hindgut, female reproductive tract, and foregut or other. Within each group subgroups of laparoscopic and open procedures will be made.
 
We expect approximately 70,000- 100,000 patients to have had abdominal or pelvic surgery in the period June 2009- June 2011. Approximately 25,000 are expected to have had prior abdominal surgery in the previous 5 years. Thus, we expect an incident population of 45,000 to 75,000 to be included in the study.

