	
For the study we will analyse re-admission in the years following surgery that are directly related to adhesions, possibly related to adhesions, and readmission with surgery that might be complicated by adhesions. For this purpose we will need a patient identifier that allows to link readmissions to the initial surgery. The data can be anonymized so that the identifier represent just a random number. As baseline characteristics we will only require age and sex. No further potentially identifiable data such as birth date, postal code or NHS number is required.
 
From the initial admission with abdominal or pelvic surgery we need ICD- 10 codes and OPCS- 4 codes describing the type of surgery performed as well as information whether the operation was performed laparoscopic ally or open. This same set of information is needed for any readmission in follow-up. Further we need the time interval (in months) between the index operation and the readmission. Only readmissions coded by one or more relevant ICD-10 or OPCS-4 code need to be included.
 
For a readmission to be classified as directly related to adhesions, an explicit adhesion reference was required in the operative OPCS-4 or diagnostic ICD-10 coding. Adhesions might however not always be coded, especially not if readmission goes without surgery. For example, a conservative treated small bowel obstruction might only be coded as abdominal pain, nausea, and vomiting. Therefore we will define a broader set of operative codes and diagnostic codes that might indicate a possibly adhesion- related complication.
 
Data from follow-up is requested to the latest date from which a complete record can be extracted.

3.1.09	Does the proposal have implications for, or target, sensitive groups or vulnerable populations? Please give details
	No
3.1.10	Does the proposal seek to use information exclusively about deceased persons? Please give details
	No

3.1.11	Have any members of the public/lay representatives been involved in the proposal design? Please give details
	No
3.1.12	Has any peer review of the proposal been undertaken? Please give details (for example formal review by a peer organisation or funding body, informal internal review, review by a third party)
	Informal internal review has been performed within the Radboud University Medical Center, department of Surgery. The research proposal and internal funding for performing the study were approved.

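### The laparoscopic/open comparison has no stated control for index procedure or diagnosis within three gross anatomical groups, although the codes for both are requested

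*Combined protocol and SAP*

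**What the plan says.** The aim in 3.1.07 is worded as an effect: "To evaluate the impact of laparoscopic surgery on adhesion- related formation". The means is a direct contrast: "Comparison of readmissions for adhesion- related complications after open and laparoscopic surgery will be made". The same item has a second, descriptive purpose: "The study will provide an estimate of the current burden of adhesion-related morbidity in Scotland".

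The analysis groups are in 3.1.08: "patients will be grossly divided in three groups of anatomical location of the surgery: hindgut, female reproductive tract, and foregut or other". The next sentence reads: "Within each group subgroups of laparoscopic and open procedures will be made". One of the three groups is a residual category.

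Some control is planned:
- Eligibility is restricted: "We will exclude patient who had had abdominal or pelvic operation in the 5 years before 2009". The reason given is that adhesions already present could affect the results.
- On covariates, 3.1.08 states: "As baseline characteristics we will only require age and sex". Section 4.3 adds that age is calculated because it may be a risk factor for adhesions.
- The anatomical split is itself a coarse control for type of operation.

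Item 3.1.08 and the table in 4.3 also request ICD-10 and OPCS-4 codes for the index admission, and whether the operation was laparoscopic or open. The uses stated for the codes are selecting the cohort, describing the surgery and classifying readmissions. The supplied text gives no regression model, finer strata, weighting or standardisation by procedure or diagnosis.

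**The concern.** Surgical approach was not randomised. The cohort takes in all initial abdominal or pelvic surgery on the code list, and 3.1.07 says that such surgery is done by several specialties. Each of the three groups can therefore hold operations, and reasons for operating, that differ in their own risk of readmission. If laparoscopy is used more for some of these than for others, the within-group contrast mixes the effect of approach with the effect of case mix.

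A large cohort does not protect against this. It narrows the interval around a biased estimate and makes a small false difference more likely to look convincing. What is at stake is the comparison that serves the impact aim. The overall burden estimate does not depend on comparing approaches and is not affected.

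**Working it through.** **The plan's own figure.** The expected cohort in 3.1.08 reproduces: 70,000 − 25,000 = 45,000 and 100,000 − 25,000 = 75,000. No significance level, power or effect size is given, so there is nothing further to reproduce.

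**Assumed inputs (not in the documents).** Equal thirds by anatomical group: 45,000/3 = 15,000, or 75,000/3 = 25,000. A 50:50 split by approach gives 7,500 or 12,500 per arm. Readmission risk averages 10%. There are two equally common procedures in a group, and laparoscopy has no effect within either.

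**Step 1: size of the false difference.** With no true effect,

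false risk difference = (difference in procedure share between approaches) × (risk gap between procedures).

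It is zero if either factor is zero.

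**Step 2: the difference that has a 50% chance of two-sided 5% significance.** This is 1.96 × √(2p(1−p)/n).
- n = 7,500: 1.96 × √(2 × 0.10 × 0.90/7,500) = 0.0096, or 0.96 percentage points.
- n = 12,500: 0.0074, or 0.74 points.

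At 7,500 per arm, a share difference of 0.4 reaches the threshold with a risk gap of 0.0096/0.4 = 2.4 points. A share difference of 0.2 needs 0.0096/0.2 = 4.8 points.

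**Step 3: two worked cases, 7,500 per arm.**

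| Case | Laparoscopic risk | Open risk | RR (95% CI) | z |
|---|---|---|---|---|
| Mild: share difference 0.2, gap 2 points | 0.6×0.09 + 0.4×0.11 = 0.098 | 0.4×0.09 + 0.6×0.11 = 0.102 | 0.96 (0.87–1.06) | −0.82 |
| Moderate: share difference 0.4, gap 4 points | 0.7×0.08 + 0.3×0.12 = 0.092 | 0.3×0.08 + 0.7×0.12 = 0.108 | 0.85 (0.77–0.94) | −3.27 |

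The true risk ratio is 1.00 in both. The mild case is not significant. If laparoscopy were used more for the higher-risk procedure, the ratios would be 1.04 and 1.17, so the direction is open as well.

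**Step 4: precision cost of stratifying.** Standard error of log RR, crude against inverse-variance stratified:
- Mild: 0.0490 to 0.0500, ratio 1.02.
- Moderate: 0.0492 to 0.0533, ratio 1.08.

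With ten equally common procedures in a group of 15,000, and risks evenly spaced from 12% to 8% as the laparoscopic share rises:
- Shares evenly spaced from 30% to 70%: 0.0490 to 0.0506, ratio 1.03.
- Shares evenly spaced from 5% to 95%: 0.0491 to 0.0598, ratio 1.22.
- Four procedures at 2%, two at 50% and four at 98%: 0.0493 to 0.0955, ratio 1.94.

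**The case against.** The strongest objection is that this is a data-access application. The prompt in 3.1.08 asks for sources, sample size, eligibility, dates and identifiability, not for statistical methods. Section 7 lists a protocol sent for IRB approval and a code appendix. Neither was supplied, and either could hold an adjustment plan or procedure categories. The statement about age in 4.3, and the request for index codes separately from approach, are both consistent with an adjusted analysis. All of this stands. It limits the point to what the supplied text states.

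It does not remove the point. The applicants used 3.1.08 to set out their analysis groups, and 3.1.07 promises an evaluation of impact. Followed as written, those groups do not support that aim. Neither age nor sex stands in for procedure or indication.

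Three stronger readings are tempting, and the documents do not support them:
- **That the comparison will be crude.** The form says that subgroups will be made. It does not say that this is the whole analysis.
- **That the unticked matched-controls box in 5.1.01 rules out adjustment.** The box sits among options for linking and supplying data. Both arms already lie within the one requested cohort, so matching, weighting or regression inside it would not need that box.
- **That the earlier SCAR result can scale the bias.** The 34.6% is a ten-year figure for readmissions directly or possibly related to adhesions. This design plans 4 to 5 years of follow-up.

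It may also be said that the remedy comes late, because 3.3.01 refers to editors' questions on how the data are presented. That affects how an adjusted analysis must be labelled, not whether it is needed.

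**Conclusion.** The point holds as a gap in the supplied plan that should be fixed, with medium confidence. The aim is worded as impact, and the one stated structure leaves index procedure and diagnosis uncontrolled within each group. Confounding follows only if approach goes with procedure or indication there. The documents give no procedure mix, so they do not show that bias is present, and they fix neither its size nor its sign.

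The illustrations show how little imbalance would matter. On the assumed inputs, a false difference of 0.96 points (0.74 in a group of 25,000) is as likely as not to be significant. A moderate imbalance gives a risk ratio of 0.85, or 1.17 with the risks reversed, when the truth is 1.00. A mild imbalance may pass unnoticed. These results rest on equal thirds, a 50:50 split, two procedures and a 10% average risk. Confidence is medium because the IRB protocol could not be read.

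**What to change.** Keep the three-group tables as a description of burden. Base the laparoscopic/open comparison on an analysis stratified by or adjusted for index OPCS-4 procedure category, index ICD-10 diagnosis class, age and sex. Define the categories in the plan. Report which procedure categories are done almost entirely by one approach, since they contribute little to the contrast. State residual confounding by urgency and comorbidity as a limitation.

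If the IRB protocol already specifies such adjustment, carry it into this plan. If results have been seen, label the adjusted analysis post hoc and show it beside the three-group tables.

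The cost is category definitions and programming. No new variables are needed, because all are already in the table in 4.3. Intervals widen: the standard error of log RR rises by about 2% to 8% under mild to moderate imbalance. It rises by more where procedures are nearly all done by one approach (22% and 94% in the two more unbalanced ten-procedure examples). These figures are for a stratified risk ratio; the cost for a full regression model was not computed. The adjusted estimate will mainly describe procedures done by both approaches, and the report should say so.

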### 4.3 Data Variables *Please read section 4.3 of the guidance*

Dataset/source Name	Variable	Time Period/Range	Processing only?
Anonymised ID			
Scottish Morbidity Record (SMR 01)	CHI	2004- Dec 2016	Yes
Scottish Morbidity Record (SMR 01)	Date of admission	2004- Dec 2016	No
Scottish Morbidity Record (SMR 01)	Sex	2009- Dec 2016	No
Scottish Morbidity Record (SMR 01)	Age (Date of admission- birth date)	2009- Dec 2016	No
Scottish Morbidity Record (SMR 01)	ICD-10 codes	2009- Dec 2016	No
Scottish Morbidity Record (SMR 01)	OPCS-4 codes	2009- Dec 2016	No
Scottish Morbidity Record (SMR 01)	Duration since index operation (date of admission from readmission - date of admission from index operation)	2009- Dec 2016	No
Scottish Morbidity Record (SMR 01)	Details of operation - laparoscopic/ open	2009- Dec 2016	No
Scottish Morbidity Record (SMR 01)	End of follow-up (month) (Date of end of follow-up, typically June 2016; however some patient might not complete follow-up because of mortality or migration)	2004- Dec 2016	No
Scottish Morbidity Record (SMR 01)	Continuous Inpatient Stay	2009- Dec 2016	No
CHI Database	Migration Month / year	2004- Dec 2016	No

NRS Deaths	Patient alive or death by end of follow-up	2004- Dec 2016 (measured in months, no date provided)	No
------------	--	---	----

Please justify your need for identifiable or potentially identifiable variables:

Identifiable data is only needed during the processing of data. Data will be collected during a range of 5 years from index surgery. Patients with a relevant OPCS-4 code as listed in the appendix are selected, if no prior such operation was found in the five years previous to the index operation. Identifiable information, NHS number and birth date are needed during processing to select reoperations that are definitely or potentially related to adhesion in patients following their index surgery. After processing these data can be removed. Age is potential risk factor for adhesions and will therefore be calculated.

4.4	NRS/NHSCR Data Sources Please read section 4.4 of the guidance	
Complete this section if access to NHSCR is required, or if there is any National Records of Scotland involvement		
4.4.01	Does the proposal require access to NHS Central Registry as a sampling frame for cohorts?	No
4.4.02	Does the proposal involve flagging of individuals on the NHSCR for long term follow up?	Choose an item.

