## Section 7 - Supporting Evidence

### **Supporting Evidence** *Please read section 7 of the guidance*

Please list each piece of supporting evidence which you have included with your application in the box below – the name of each should clearly indicate what the document/file/reference is about

- Appendix with list of OPCS 4.7 and ICD10 codes relevant for selection of data
- Certificates of Research data and confidentiality training
- Protocol as send for IRB approval
- IRB approval
- Privacy Impact assessment

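### Route has only two levels and no rule covers vaginal, transanal or perineal operations; if these are in the cohort and counted as open, the laparoscopic/open contrast may be biased

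*Combined protocol and SAP*

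**What the plan says.** **Scope.** Item 3.1.08 states: "Inclusion criteria are all patients undergoing initial abdominal or pelvic surgery between June 2009 and June 2011". After the exclusion for earlier abdominal or pelvic surgery it adds: "There are no further exclusion criteria". Nothing in the text excludes an operation by route.

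**Selection.** Scope is put into practice through OPCS-4 codes: "A list of relevant codes can be found in the appendix". Section 7 lists this as an attachment, "Appendix with list of OPCS 4.7 and ICD10 codes relevant for selection of data". Its contents are not part of the reviewed text.

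**Groups.** Patients are divided into "hindgut, female reproductive tract, and foregut or other".

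**Route.** Route appears in three places, each time with two levels:
- the analysis in 3.1.08: "Within each group subgroups of laparoscopic and open procedures will be made";
- the data request in 3.1.08: "information whether the operation was performed laparoscopic ally or open";
- the extract in Table 4.3: "Details of operation - laparoscopic/ open".

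Vaginal, transanal and perineal routes are not mentioned. The OPCS-4 codes of the index operation are requested separately in 3.1.08 and Table 4.3. Item 3.1.07 makes the comparison of open with laparoscopic surgery central to the study.

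**The concern.** Some pelvic operations are done neither by laparoscopy nor through an incision in the abdominal wall. Vaginal hysterectomy and prolapse repair would fall in the female reproductive tract group, and transanal or perineal rectal procedures in the hindgut group. This is a different problem from laparoscopies converted to open surgery, because these patients never had a laparotomy.

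A two-level field has no correct place for them, which leaves two outcomes:
- They are called open because they carry no laparoscopic label. The open group then mixes laparotomy with something else.
- They are left unclassified and drop out of the comparison. The route subgroups then no longer add up to their anatomical group.

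Without a written rule, the choice may be made after the data are seen. The only baseline characteristics requested are age and sex, and adjusting for these cannot repair a mixed comparator. The expected cohort is large, so a systematic shift would not be hidden by sampling error, and the confidence intervals would not reflect it.

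**Working it through.** **1. The plan's own figure.** Item 3.1.08 expects 70,000 to 100,000 operated patients, less about 25,000 with prior surgery.
- 70,000 − 25,000 = 45,000
- 100,000 − 25,000 = 75,000

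The stated incident population of 45,000 to 75,000 reproduces. There is no split by route, no effect size and no power calculation to check. A third route class does not change this total.

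**2. Model for the case where other-route operations are counted as open.** Let f be their share of the recorded open group. Let p_O, p_L and p_V be the risks after laparotomy, laparoscopy and other routes.
- Observed open risk = (1 − f) × p_O + f × p_V
- Observed RR = p_L / observed open risk

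With k = p_V / p_O, dividing through by p_O gives:
- Observed RR = true RR / [1 − f × (1 − k)]

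The baseline risk cancels, so the distortion of the ratio depends only on f and k. The one readmission figure in the documents (34.6% over 10 years, item 3.1.07) therefore cannot settle its size. The documents give neither f nor k, so every input below is an assumption.

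**3. Illustration.** Assume p_O = 5%, p_L = 3% and p_V = 2%, so the true RR is 0.60 and k = 0.4. For f = 20%, observed open risk = 0.8 × 5% + 0.2 × 2% = 4.4%, and 3% / 4.4% = 0.68. The last column sets p_L = 5%, so that the true RR is 1.

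| f | Observed open risk | Observed RR (true 0.60) | Observed RR (true 1.00) |
|---|---|---|---|
| 10% | 4.7% | 0.64 | 1.06 |
| 20% | 4.4% | 0.68 | 1.14 |
| 30% | 4.1% | 0.73 | 1.22 |
| 40% | 3.8% | 0.79 | 1.32 |

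**4. Dependence on the assumed other-route risk.** Observed RR when the true RR is 0.70:

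| k | f = 10% | 20% | 30% | 40% |
|---|---|---|---|---|
| 0.25 | 0.76 | 0.82 | 0.90 | 1.00 |
| 0.50 | 0.74 | 0.78 | 0.82 | 0.88 |
| 0.75 | 0.72 | 0.74 | 0.76 | 0.78 |
| 1.00 | 0.70 | 0.70 | 0.70 | 0.70 |
| 1.25 | 0.68 | 0.67 | 0.65 | 0.64 |

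The estimate moves toward the null when k is below 1, stays put when k = 1, and moves away from the null when k is above 1. It can also cross the null. With a true RR of 0.85 and k = 0.5, the observed RR is 0.89, 0.94, 1.00 and 1.06 for the same values of f.

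**5. The other outcomes.** If these operations are not in the code list, or are dropped from the comparison, then f = 0 and the observed RR equals the true RR in every row.

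**The case against.** The strongest reply is that the documents do not show the problem occurring.

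- **Inclusion.** Eligibility is fixed by a code list. A list can leave out vaginal, transanal and perineal procedures without any separate exclusion criterion, so the absence of further exclusions does not prove that they are in. Their share could be zero. That the list is not in the reviewed text is no fault of the plan. The IRB protocol named in Section 7 was also not available and may define route.
- **Default to open.** No section says that open means everything not labelled laparoscopic.
- **Direction.** Item 3.1.07 links minimal invasive surgery to less peritoneal injury and fewer adhesions. Extending that reasoning to a vaginal or transanal approach is plausible, but it is an inference. No risk by route is given.
- **Data.** The OPCS-4 codes are already requested, so route could be refined at analysis.

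The first three points stand, and they rule out a stronger reading. A reader might infer from the broad scope and the two-level field that vaginal operations definitely dilute the open group and hide a benefit of laparoscopy. The documents establish neither inclusion, nor assignment to open, nor a lower risk. Having no class and diluting the open group are also alternative outcomes and cannot both happen to the same operation.

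The fourth point shows that a remedy is available. It does not show that one is planned.

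**Conclusion.** The gap is in the text: a scope worded to cover all pelvic surgery, a female reproductive tract group, two route levels wherever route appears, and no rule for an operation that is neither. The change should be made, because it bears on the main comparison and costs little.

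The bias is conditional on three things: the code list includes such operations, they are counted as open, and their risk differs from that after laparotomy. Where all three hold, the effect would fall mainly in the female reproductive tract group. The movement from 0.60 to between 0.64 and 0.79 illustrates the possible size; it is not an estimate, since the 5%, 3% and 2% risks and the 10% to 40% share are all assumed. Confidence is moderate: high that no rule is stated, low on how far any estimate would move.

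**What to change.** In 3.1.08:

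1. Define open as laparotomy.
2. Derive a third index-route class (vaginal, transanal or perineal) from the OPCS-4 codes already requested, and list the codes that define it. State where laparoscopically assisted vaginal operations belong; the laparoscopic class is the natural choice.
3. Restrict the laparoscopic/open comparison to the first two classes.
4. Report the third class separately in the burden estimates, so that the route classes add up to each anatomical group.
5. If the code list already leaves these operations out, say so in one sentence; nothing else is then needed.

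The cost is a split of the code list, a few sentences, and a smaller open subgroup. No new variable is needed in Table 4.3.

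### With no index admission type and no pre-index diagnoses requested, the laparoscopic/open comparison can be only partly adjusted for case mix, and differences in urgency or prior illness could appear as an effect of route.

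*Combined protocol and SAP*

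**What the plan says.** Section 3.1.07 aims to assess what laparoscopic surgery has done to adhesion-related morbidity: "Comparison of readmissions for adhesion- related complications after open and laparoscopic surgery will be made". Route of surgery was not randomised.

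Section 3.1.08 describes how case mix is handled. Patients fall into three broad anatomical groups (hindgut, female reproductive tract, foregut or other), and "Within each group subgroups of laparoscopic and open procedures will be made". Apart from abdominal or pelvic surgery in the preceding five years, "There are no further exclusion criteria", so emergency and elective index operations both enter.

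On covariates, section 3.1.08 says "As baseline characteristics we will only require age and sex". It goes on to request more from the index stay: "From the initial admission with abdominal or pelvic surgery we need ICD- 10 codes and OPCS- 4 codes describing the type of surgery performed". Table 4.3 lists the SMR01 items: CHI, admission date, sex, age, ICD-10 codes, OPCS-4 codes, time since index operation, route ("Details of operation - laparoscopic/ open"), end of follow-up, and "Continuous Inpatient Stay". Admission type is not among them, nor is a comorbidity measure. The ICD-10 and OPCS-4 rows run from 2009. The only risk factor for which a reason is given is age: "Age is potential risk factor for adhesions and will therefore be calculated". The reviewed text describes no adjustment model.

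**The concern.** Urgency and general health plausibly influence both the choice of an open operation and the chance of a later abdominal readmission. That is an assumption, since the documents give no data on it. If it holds, the open arm contains more urgent and sicker patients, and a lower readmission rate after laparoscopy may partly or wholly reflect who was operated on by which route.

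The gap lies in the data request. If admission type and earlier diagnoses are not extracted, no later model can use them. Section 3.1.07 notes that many surgeons already consider further adhesion prevention unnecessary with laparoscopy. A case-mix artefact in laparoscopy's favour would reinforce the belief that the study is meant to examine.

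**Working it through.** **1. The plan's own figure.** Section 3.1.08 expects 70,000-100,000 operated patients, of whom about 25,000 had prior surgery. 70,000 − 25,000 = 45,000 and 100,000 − 25,000 = 75,000, so the stated incident population of 45,000 to 75,000 reproduces. The reviewed text states no significance level, power or effect size. The only outcome rate is 34.6% over 10 years, for directly or possibly related readmissions in the earlier Scottish study (section 3.1.07).

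**2. What the requested variables can and cannot adjust for.**

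| Factor | Source in the request | Adjustment possible |
|---|---|---|
| Age, sex | Table 4.3 | Yes |
| Procedure, indication | Index OPCS-4 and ICD-10 codes | Yes, though no plan to do so is stated |
| Illness coded at the index stay | Index ICD-10 codes | Partly |
| Emergency or elective | No field | Only by proxy, through acute diagnoses |
| Illness before the index stay | ICD-10 from 2009; codes wanted for the index stay and for relevant readmissions | Not adequately |

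The proxy for urgency is incomplete because the same procedure for the same diagnosis can be done electively or as an emergency.

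**3. Possible size of the bias (all inputs assumed).** Let pL and pO be the emergency shares in the laparoscopic and open arms, and R the risk multiplier for emergency surgery. With no true effect of route:

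apparent RR = [1 + pL(R − 1)] / [1 + pO(R − 1)]

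- Middle case, pO = 0.50, pL = 0.25, R = 2: 1.25/1.50 = 0.83.
- Mildest case, pO = 0.40, pL = 0.25, R = 1.5: 1.125/1.20 = 0.94.
- Strongest case, pO = 0.60, pL = 0.20, R = 2.5: 1.30/1.90 = 0.68.

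A lower set of assumptions (open 30-50%, laparoscopic 10-20%, R 1.25-2.0) gives 0.977 to 0.733. These figures are for a comparison without adjustment for urgency. Adjustment through index codes would remove an unknown part.

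**4. Set against chance.** Assume an even split over three groups and two routes: 45,000/6 = 7,500 or 75,000/6 = 12,500 per arm. Assume also a 5% risk p. The 95% range around a true ratio of 1 is exp(±1.96·√[2(1 − p)/(m·p)]):

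- m = 7,500: exp(±1.96 × 0.0712) = 0.87 to 1.15.
- m = 12,500: exp(±1.96 × 0.0551) = 0.90 to 1.11.

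A value of 0.83 lies outside both ranges and 0.94 lies inside both.

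**5. Chance that a pure-bias ratio is declared significant.** The test is two-sided at 5% (assumed), for risks of 5.00% (open) and 5.00% × 0.833 = 4.17% (laparoscopic), a difference of 0.00833. Power is approximately Φ(difference/SE − 1.96).

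- m = 7,500: SE = √[(0.0475 + 0.0399)/7,500] = 0.00341; Φ(2.44 − 1.96) = 0.69.
- m = 12,500: SE = 0.00264; Φ(3.15 − 1.96) = 0.88.

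With 30% laparoscopic instead of 50%, the same calculation gives 0.60 and 0.82. For a ratio of 0.94 the probability is 0.12 to 0.21 over the same settings. The result depends on the event risk. With equal routes, 0.83 is detected with probability 0.33-0.50 at 2% risk and almost always at 20%.

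**The case against.** The strongest objection is that the sentence on age and sex belongs to a data-minimisation argument and is not a covariate list. The sentences that follow it request the index diagnoses and procedures. A reader might infer that nothing extracted can separate sicker from healthier patients, or that prior illness cannot be corrected for at all. The documents do not support that. Procedure, indication and illness coded at the index stay are available, and acute diagnoses carry some information on urgency. What remains is that this adjustment is incomplete and that the reviewed text does not plan it.

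A reader might also infer that a spurious 0.83 is certain to be reported as significant, or that the plan is known to favour laparoscopy. Neither follows. The first is probable only under the stated assumptions. The second rests on emergency shares and a risk multiplier that appear nowhere in the documents and may differ between the anatomical groups.

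Three further points have some weight.

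- The 2009 start of the code rows cannot describe all the processing, because the check for prior operations must reach back about five years and the OPCS-4 row also starts in 2009. Even so, no diagnostic look-back is requested.
- Section 7 lists the protocol sent for IRB approval and the code appendix, neither of which is in the reviewed text. An adjustment plan based on index codes could be there, but it could not use fields that Table 4.3 omits.
- Section 3.3.01 extends access to answer a journal's questions on data presentation, which suggests that the data have already been drawn. That raises the cost of a change but does not remove the gap.

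**Conclusion.** The point holds in this form: the laparoscopic/open comparison cannot be adequately corrected for urgency of the index operation or for prior comorbidity, and the reviewed text names no adjustment set. Case mix could therefore appear as an effect of route. That the apparent ratio would fall below 1 rests on assuming that open patients are more often emergencies and that emergency surgery raises readmission risk. The mild end of the illustrated range would mostly pass as chance at 5% risk. The middle and strong parts could well be read as a real benefit. The overall estimate of adhesion-related burden, the plan's other aim, does not depend on this comparison and is unaffected.

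**What to change.** Replace the age-and-sex sentence in section 3.1.08 and add two non-identifying categorical variables to Table 4.3:

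1. Admission type of the index stay (emergency or elective), if the data controller confirms that SMR01 holds it. The documents do not say.
2. A comorbidity category that the data controller derives from SMR01 ICD-10 codes in the five years before the index operation. The earlier codes would be for processing only, which keeps to the plan's data-minimisation stance.

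State in the plan that, within each anatomical group, the laparoscopic/open comparison is adjusted for age, sex, index procedure, indication, comorbidity category and urgency, with results also shown separately for elective and emergency index surgery. Keep the all-patient comparison as planned; making an elective-only comparison the main one would change the target population.

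The cost is a slightly larger data request to justify, or an amended extraction with its approvals if the data have already been drawn. If the fields cannot be obtained, adjust for the index procedure and diagnosis codes already requested, and state residual confounding by urgency as a limit on any causal conclusion about route.
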